### **12.3.7. Some Statistical Considerations**

Censoring Criteria for Time to Events:

When there is no occurrence of the event, time to event will be censored to the date of last event assessment (last visit, death, or date of ET).

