## 9. ASSESSMENTS AND ENDPOINT DEFINITIONS

### 9.1. Endpoint Definitions

#### 9.1.1. VTE Endpoints

A suspected new or progressive symptomatic VTE, in the same anatomical region, should be documented with the same imaging method used at Screening/Baseline. Suspected new or progressive VTE in a different anatomical region should be documented utilizing institutional standards. These images should be collected and be included in the primary source records. Thrombus resolution of the qualifying event will be measured by repeat imaging at the EOS visit (using the same modality as that which was used to diagnosis the thrombosis prior to enrollment). If an image has been captured prior to the EOS and it demonstrates complete resolution of the qualifying VTE, then a repeat image does not need to be done again at day 90. For purposes of the study, the complete resolution image will be the “EOS” image for the index event.

In the assessment of a new or progressive symptomatic thrombus, the following general definitions will be utilized;

**Symptomatic New VTE:** Symptomatic VTE confirmed by at least one radiographic test. Asymptomatic VTE within a venous segment noted to be patent on a prior imaging study. Symptomatic will be defined as: New or progressive signs and symptoms as judged by the investigator including but not limited to:

- Objective swelling;
- Pain or tenderness;
- Pitting edema;
- Erythema or cyanosis.

**All New VTE:** All VTE confirmed by at least one radiographic test.

**Stable VTE:** Follow-up study demonstrating stable clot burden utilizing the same imaging modality as the Screening Visit.

**Regression of VTE:** Follow-up study demonstrating regressed clot burden utilizing the same imaging modality as the Screening Visit.

**Progression of VTE:** Progression of clot burden on a follow-up study in terms of severity of occlusion, or involvement of new venous segments at any time after the initial diagnosis.

In the assessment of a new or recurrent PE, the following general definitions will be utilized;

**New PE:** Symptomatic PE confirmed by presence of an intraluminal filling defect of the pulmonary artery on CT angiography and/or a mismatched defect on a nuclear V/Q scan. All new PE's will be considered to be a symptomatic event.

**Stable PE:** Follow-up study demonstrating stable clot burden utilizing the same imaging modality as the Screening Visit.

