#### **PE Specific Definition:**

To meet the criteria for new or progressive PE one of the following criteria must be met:

1. A new intraluminal filling defect or a sudden cut-off of vessels more than 2.5 mm in diameter on a pulmonary angiogram.

2. An intraluminal filling defect on CT angiography involving the main pulmonary artery, or proximal generations of the branch pulmonary arteries that are reliably evaluated by CT.
3. High probability V/Q scans.

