#### ***MAJOR BLEEDING (Composite of the following)***

- a. Fatal bleeding.
- b. Clinically overt bleeding associated with a decrease in Hgb of at least 2 g/dL in 24 hours.
- c. Overt bleeding deemed by the attending physician to be unrelated to the subject's underlying condition and accompanied by blood product administration.
- d. Overt bleeding which is retroperitoneal, intracranial, intraspinal, intraocular, or intra articular.
- e. Overt bleeding deemed by the attending physician to necessitate permanent discontinuation of trial medication.

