#### **10.12.1. Serious Adverse Event Reporting Requirements**

If an SAE occurs, Pfizer is to be notified within 24 hours of investigator awareness of the event.

In particular, if the SAE is fatal or life-threatening, notification to Pfizer must be made immediately, irrespective of the extent of available AE information. This time frame also applies to additional new information (follow-up) on previously forwarded SAE reports as well as to the initial and follow-up reporting of EDP, exposure via breastfeeding, and occupational exposure cases.

In the rare event that the investigator does not become aware of the occurrence of an SAE immediately (eg, if an outpatient study subject initially seeks treatment elsewhere), the investigator is to report the event within 24 hours after learning of it and document the time of his or her first awareness of the AE.

For all SAEs, the investigator is obligated to pursue and provide information to Pfizer in accordance with the time frames for reporting specified above. In addition, an investigator may be requested by Pfizer to obtain specific additional follow-up information in an expedited fashion. This information collected for SAEs is more detailed than that captured

on the AE CRF. In general, this will include a description of the AE in sufficient detail to allow for a complete medical assessment of the case and independent determination of possible causality.

Information on other possible causes of the event, such as concomitant medications, vaccines, and/or illnesses, must be provided. In the case of a subject death, a summary of available autopsy findings must be submitted as soon as possible to Pfizer or its designated representative.

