## **9. APPENDICES**

### **Appendix 1. STATISTICAL METHODOLOGY DETAILS**

#### **Appendix 1.1. Time to Event**

For this analysis, time to event will be measured from the first dose of study medication in days. For subjects who have event, time to event is defined as:

$$T = \text{date of event} - \text{first treatment date} + 1$$

Subjects who do not have the event of interest will be censored at the latest date in the database. Time to event is defined as:

$$T = \text{latest date in the database} - \text{first treatment date} + 1$$

The latest date is expected to be the date of the End of Study visit.

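### A fatal pulmonary embolism proven at autopsy but never imaged is scored as no VTE, whereas fatal bleeding counts as major bleeding

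*Protocol*

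**What the plan says.** **VTE case definition.** Protocol 9.1.1 defines symptomatic new VTE as "Symptomatic VTE confirmed by at least one radiographic test". A new PE must be "confirmed by presence of an intraluminal filling defect of the pulmonary artery on CT angiography and/or a mismatched defect on a nuclear V/Q scan". The PE-specific list opens with "To meet the criteria for new or progressive PE one of the following criteria must be met" and then gives three routes: pulmonary angiogram, CT angiography and high-probability V/Q scan. Section 4 words the VTE endpoint as needing the same objective technique as at baseline.

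**Analysis.** SAP 6.1.2.1 reports the proportion with new or progressive symptomatic VTE. It also fits a logistic model in which only a child with such an event is coded Yes, and plans Kaplan-Meier and Cox analyses of time to first recurrent VTE. All of these use the PD population.

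**Censoring.** Protocol 12.3.7 says that, without an event, "time to event will be censored to the date of last event assessment (last visit, death, or date of ET"). SAP Appendix 1.1 says "Subjects who do not have the event of interest will be censored at the latest date in the database" and does not mention death.

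**Bleeding.** The first component of major bleeding in Protocol 9.1.2 is "Fatal bleeding", with no imaging condition.

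**Autopsy.** Protocol 10.12.1 states: "In the case of a subject death, a summary of available autopsy findings must be submitted as soon as possible to Pfizer". This is a safety-reporting duty and is not linked to the VTE endpoint.

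**The concern.** Sudden death is one way in which anticoagulation can fail, and a child who dies suddenly may never reach a scanner. Autopsy is then the objective evidence of what happened, and the sponsor already asks for it. Yet the stated PE criteria give that evidence no standing, so the rules return a definite answer, and it is the wrong one: no VTE.

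The fault is one-directional, because a missed fatal PE can only lower the reported VTE risk. It is also asymmetric. SAP 6.1.2.1 and 6.3.1 fit parallel logistic models of new or progressive VTE and of major bleeding on the anti-Xa level at the end of dose adjustment. In those models a fatal clot seen only at autopsy would be coded No and a fatal bleed Yes.

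**Working it through.** **1. Is there a figure of the plan to reproduce?** None depends on this point. The target of 50 comes from population PK/PD trial simulation (Protocol 12.1), not from any VTE or bleeding rate. I use 50 below only as an illustrative size for the PD population.

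**2. Follow one child through the rules.** Suppose a child reaches the anti-Xa target, and so is in the PD population, then dies on dalteparin. Autopsy shows a PE and no imaging was done.

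| Step | Rule | Result |
|---|---|---|
| Is it a new or progressive PE? | Protocol 9.1.1: CT angiography, V/Q scan or pulmonary angiogram | No |
| Proportion with VTE | SAP 6.1.2.1 | In the denominator, not in the numerator |
| Logistic model | SAP 6.1.2.1: Yes only with a new or progressive VTE | No |
| Kaplan-Meier and Cox | Protocol 12.3.7 | Event-free, censored at death |
| The same, under the SAP | SAP Appendix 1.1 | Event-free, censored at the latest database date |
| If the death were from bleeding | Protocol 9.1.2 | Major bleeding event |

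The no-imputation rule in SAP 5.3 does not alter this, because the child is classified and not missing.

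**3. Effect on the proportion.** The SAP's interval is Clopper-Pearson. For x events in n, the lower limit is the 2.5% quantile of Beta(x, n − x + 1), or 0 when x = 0. The upper limit is the 97.5% quantile of Beta(x + 1, n − x).

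| Imaged VTEs | Autopsy-only fatal PEs | As written | Death counted |
|---|---|---|---|
| 0 | 1 | 0/50 = 0% (0 to 7.1%) | 1/50 = 2.0% (0.05 to 10.6%) |
| 2 | 1 | 2/50 = 4.0% (0.5 to 13.7%) | 3/50 = 6.0% (1.2 to 16.5%) |

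Each such death is worth 1/50 = 2 percentage points. In an illustrative age group of 10, one death moves 0/10 (0 to 30.9%) to 1/10 = 10% (0.25 to 44.5%).

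**4. Effect on Kaplan-Meier.** Assume no other censoring before Day 90. With no imaged VTE and one such death, the Day 90 incidence is 0% if the death is censored and 1 − 49/50 = 2.0% if it is counted. With two earlier imaged VTEs, it is 1 − 48/50 = 4.0% against 1 − (48/50)(47/48) = 6.0%.

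**5. How likely is it to arise?** The documents give no rate. If p is an assumed per-child risk of such a death, the chance of at least one in 50 is 1 − (1 − p)^50. This is 22% at p = 0.5%, 64% at p = 2% and 87% at p = 4%. These values of p are assumptions that span a range, not estimates.

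**6. Deaths from other causes.** Take a 5% one-minus-Kaplan-Meier VTE risk and assume 2 to 10% other-cause mortality (d) by Day 90, with constant hazards h1 = −ln(0.95) and h2 = −ln(1 − d). The cumulative incidence is h1/(h1 + h2) × [1 − exp(−(h1 + h2))]. It equals 4.95% at d = 2% and 4.75% at d = 10%, a change of at most 0.25 points. The exact interval for 2/50 is 13.7 − 0.5 = 13.2 points wide.

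**The case against.** The best defence is that Protocol 12.3.7 is an ordinary censoring rule. It applies only when the event has not occurred, so if an autopsy-proven PE were a defined event, the rule would already handle it. That is right, and it puts the cause in 9.1.1. A reader might infer that naming death as a censoring date is itself the error; the documents do not support that.

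A reader might also infer that no VTE can be recorded without imaging. That goes too far: the third DVT criterion in 9.1.1, the presence of intraluminal thrombus, names no modality. The closed list applies to PE. The allowance for institutional diagnostic standards in 9.1.1 and 9.1.10 does not open an autopsy route, because both places still call for images.

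Nor do the documents support saying that the trial loses its ability to weigh clotting against bleeding. No such formal comparison is planned, the VTE objective is exploratory, and SAP 5.1 tests no hypotheses. A fatal PE would not vanish from the report either, since it would be a serious adverse event. That does not correct the VTE endpoint or its models.

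Finally, counting every death that someone attributes to VTE would bring its own bias. The trial is open-label, its adjudication committee was removed (Protocol Document History), and some children have active cancer. This stands. It limits the main analysis to autopsy-confirmed cases and leaves attributed deaths to a sensitivity analysis.

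**Conclusion.** The point holds for fatal PE confirmed at autopsy but not imaged, in a child who is in the PD population and on dalteparin at the time. Applied as written, the case definition scores that child as having no VTE, and the time-to-event analyses then censor the child event-free. A fatal bleed is counted.

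The direction of the error is certain if such a death occurs. Its size is 2 percentage points per death at an illustrative 50 children; whether one will occur cannot be judged from the documents. A child who dies before reaching the anti-Xa target is outside these analyses altogether. The primary PD endpoints and the sample size are unaffected.

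A reader might take the censoring of other-cause deaths as a second material flaw. On the assumptions shown, it is too small to matter here.

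**What to change.** 1. **Protocol 9.1.1 and SAP 6.1.2.1.** Count fatal VTE confirmed at autopsy, with death on dalteparin treatment, as a new or progressive symptomatic VTE on the date of death. Apply this in the proportion, logistic, Kaplan-Meier and Cox analyses. Changing the SAP alone would leave it in conflict with the imaging-only PE criteria, and the same-technique wording in Protocol section 4 needs a matching exception.
2. **Sensitivity analysis.** Also count deaths that the investigator attributes to VTE without imaging or autopsy.
3. **SAP Appendix 1.1.** Align the censoring date with Protocol 12.3.7, and state that only children without an event as defined in step 1 are censored at death.
4. **Optional.** Report cumulative incidence with other deaths as a competing event.

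The cost is wording in both documents, plus a defined route for autopsy information from serious adverse event reports into the analysis data. Protocol 10.12.1 requests only such autopsy findings as are available, so some deaths will remain unclassifiable; step 2 covers those that the investigator attributes to VTE. The reported VTE figure may become slightly less favourable.

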## **13. DATA MONITORING COMMITTEE**

This study will not use a data monitoring committee.

It should be emphasized that the subject, the subject's parent and/or legal representative are at liberty to withdraw their consent to participate at any time, without penalty or loss of benefits to which the subject is otherwise entitled. Subjects, their parents and/or legal representatives, who refuse to give, or withdraw, written informed consent may not be included or continued in this study, but this will not impact their subsequent care.

### **13.1. Institutional Review Board/Ethics Committee**

It is the responsibility of the investigator to have prospective approval of the study protocol, protocol amendments, informed consent/assent documents, and other relevant documents, eg, recruitment advertisements, if applicable, from the IRB/EC. All correspondence with the IRB/EC should be retained in the investigator file. Copies of IRB/EC approvals should be forwarded to Pfizer.

The only circumstance in which an amendment may be initiated prior to IRB/EC approval is where the change is necessary to eliminate apparent immediate hazards to the subjects. In that event, the investigator must notify the IRB/EC and Pfizer in writing immediately after the implementation.

### **13.2. Ethical Conduct of the Study**

The study will be conducted in accordance with legal and regulatory requirements, as well as the general principles set forth in the International Ethical Guidelines for Biomedical Research Involving Human Subjects (Council for International Organizations of Medical Sciences 2002), Guidelines for Good Clinical Practice (GCP), International Conference on Harmonisation (ICH 6), and the Declaration of Helsinki (World Medical Association (1996 & 2008)).

In addition, the study will be conducted in accordance with the protocol, the ICH guideline on GCP, and applicable local regulatory requirements and laws.

### **13.3. Subject Information and Consent**

Protection and safety of vulnerable subjects (including illiterate subjects) will be ensured to uphold the subjects' well-being, rights, and confidentiality and the integrity of their data will be safeguarded. This includes both consent procedures and methods to ensure the veracity of study assessments.

All parties will ensure protection of subject personal data and will not include subject names or other identifiable data in any reports, publications, or other disclosures, except where required by law.

When study data are compiled for transfer to Pfizer and other authorized parties, subject names, addresses, and other identifiable data will be replaced by a numerical code based on a numbering system provided by Pfizer in order to de-identify study subjects. The study site will maintain a confidential list of subjects who participated in the study, linking each subject's numerical code to his or her actual identity. In case of data transfer, Pfizer will maintain high standards of confidentiality and protection of subjects' personal data consistent with applicable privacy laws.

The informed consent/assent documents must be in compliance with ICH GCP, local regulatory requirements, and legal requirements, including applicable privacy laws.

The informed consent/assent documents used during the informed consent process must be reviewed and approved by the sponsor, approved by the IRB/EC before use, and available for inspection.

The investigator must ensure that each study subject or his or her legally acceptable representative, or parent(s) or legal guardian if a minor, is fully informed about the nature and objectives of the study and possible risks associated with participation.

Whenever consent is obtained from a subject's legally acceptable representative/parent(s) or legal guardian, the subject's assent (affirmative agreement) must subsequently be obtained when the subject has the capacity to provide assent, as determined by the IRB/EC. If the investigator determines that a subject's decisional capacity is so limited he/she cannot reasonably be consulted, then, as permitted by the IRB/EC and consistent with local regulatory and legal requirements, the subject's assent may be waived with source documentation of the reason assent was not obtained. If the study subject does not provide his or her own consent, the source documents must record why the subject did not provide consent (eg, minor, decisionally impaired adult), how the investigator determined that the person signing the consent was the subject's legally acceptable representative, the consent

signer's relationship to the study subject (eg, parent, spouse), and that the subject's assent was obtained, or waived. If assent is obtained verbally it must be documented in the source documents.

If the study includes minor subjects who reach the age of majority during the study, as recognized under local law, they must re-consent as adults to remain in the study. If the enrollment of 'emancipated minors' is permitted by the study age criteria, the IRB/EC, and local law, they must provide documentation of legal status to give consent without the permission of a parent or legal guardian.

The investigator, or a person designated by the investigator, will obtain written informed consent from each subject or the subject's legally acceptable representative, parent(s) or legal guardian and the subject's assent, when applicable, before any study-specific activity is performed, unless a waiver of informed consent has been granted by an IRB/EC. The investigator will retain the original of each subject's signed consent/assent document.

#### **13.4. Subject Recruitment**

Advertisements approved by IRBs/ECs and investigator databases may be used as recruitment procedures. Pfizer will have an opportunity to review and approve the content of any study recruitment materials directed to potential study subjects before such materials are used.

#### **13.5. Reporting of Safety Issues and Serious Breaches of the Protocol or ICH GCP**

In the event of any prohibition or restriction imposed (ie, clinical hold) by an applicable competent authority in any area of the world, or if the investigator is aware of any new information that might influence the evaluation of the benefits and risks of the investigational product, Pfizer should be informed immediately.

In addition, the investigator will inform Pfizer immediately of any urgent safety measures taken by the investigator to protect the study subjects against any immediate hazard, and of any serious breaches of this protocol or of ICH GCP that the investigator becomes aware of.

### **14. TREATMENT COMPLIANCE**

#### **14.1. Drug Accountability Procedures**

An Investigational Product Accountability Log must be kept current and available for inspection by the clinical trial monitor, and should contain the following information:

- Initial Inventory upon receipt of study drug and clinical supplies at the clinical study site;
- The identification number of each subject to whom study drug was administered;
- The date(s), quantities, lot numbers, and the dispenser's initials for all study drug administered;
- Running and final inventory (upon completion of the clinical study).

This inventory must be available for inspection by the clinical trial monitor.

Following the closeout of the study, all unused clinical supplies are to be destroyed on site or shipped by the monitor to Pfizer Inc's designated drug destruction site.

#### **14.2. Receipt of Study Drug**

The Investigator (or Pharmacist, as appropriate) must maintain records of the delivery of the study medication to the study site, the inventory at the site, the use for each subject, and the return to a delegate of Pfizer Inc.

#### **14.3. Handling of Study Drug**

All drug supplies for this study must be stored according to labeled storage conditions. If any excursion from the recommended storage (per study drug label) occurs, the study monitor or other sponsor study team member must be consulted before using the study drug.

#### **14.4. Records of Study Drug**

Study Drug will be dispensed at Baseline, Dose Adjustment Phase, PD Phase, Follow-Up and Unscheduled Visits as appropriate, and returned at Dose Adjustment Phase, PD Phase, Follow-Up and Unscheduled Visits as appropriate and End of Study. All drug dispensation and return will be documented on the IP Accountability Log. The Drug Dispensing Log must be available for monitoring, auditing, and inspection.

### **15. STUDY MANAGEMENT AND ADMINISTRATION**

#### **15.1. Monitoring**

Pfizer Inc, or designee, will perform all monitoring functions. Monitors will work in accordance with Pfizer monitoring Standard Operating Procedures (SOPs) or the SOPs of the contract research organization, as designated in the contract. Monitors will be responsible for establishing and maintaining regular contact between the Investigators and the Sponsor. Monitors will also control adherence to the protocol at the Investigative sites.

Monitors will evaluate the competence of each study site. Monitors will inform Pfizer Inc regarding problems relating to facilities, technical equipment, or medical staff. Monitors will arrange for the supply of study drug and ensure appropriate storage conditions are maintained. Monitors will ensure that written informed consent/assent has been correctly obtained from all subjects/responsible party prior to administration of any study procedures or drug administration and during the study will ensure that data are recorded correctly and completely in the CRF.

Monitoring visits will be made to each center approximately every 6 to 8 weeks and may need to occur more or less frequently if deemed necessary by Pfizer Inc. In addition, the Monitor will maintain regular contact with the site to follow study progress including subject disposition and occurrence of SAEs. The Monitor will make written reports to Pfizer Inc on each visit made to the Investigative site.

During monitoring visits, original source documents will be compared to entries in the CRF. For all subjects, monitoring of source data documentation will occur at 100%. The Monitor should have access to laboratory test reports and other subject records needed to verify the entries on the CRF. The Investigators (or his/her designee) agree to cooperate with the Monitor to ensure that any problems detected in the course of these monitoring visits are resolved.

